2.2.1. Nested Case-Control Study Design Rationale

Given the recognized limitations of assessing food intake and treatment adherence in large observational studies conducted over several months, the feasibility of collecting food intake and treatment adherence data within the cohorts will be further explored. Options to be explored will include using one of the accepted methods of measuring ARV treatment adherence and pill intake with food in a smaller sample of patients within the HIV cohorts. A nested case-control design was selected to improve computational and operational efficiency of comparisons of virologic failure as a function of adherence to treatment and food recommendations. This design also facilitates the selection of a comparison group with similar clinical experience with respect to potential confounders.

3. STUDY POPULATION

3.1. Patient Selection

The study population will be drawn from the population of patients enrolled in one or more European HIV cohorts. Eligible patients must be new users of RPV-containing regimens at the initiation of therapy (inception cohort). Patients eligible for the comparator cohort must be new users of EFV-containing regimens. Data will be included for analysis based on the availability of RPV-containing regimens in each country. Patients in the EFV-treated group will be eligible for selection from each HIV cohort if they initiate an EFV-containing regimen after the availability of an RPV-containing regimen is observed within the respective cohort. The study period will start at the date of market availability of RPV-containing regimens in the participating counties and will end when in total 600 patients from each treatment group (RPV and EFV) have been included in the study and followed for 12 months, until virologic failure, or lost to follow-up, whichever occurs first.

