Virological response to highly active antiretroviral therapy (HAART) regimens has been evaluated among patients enrolled in large, observational HIV cohorts. These studies have included evaluations of NNRTI and protease inhibitor (PI)-containing regimens (Paredes, 2000; Cozzi-Lepri, 2002) as well as short term and long term virological response when treated with NNRTI or PI-based HAART regimens (Mocroft, 2006). A few cohort studies have specifically examined virological failure among patients initiating nevirapine (NVP)-containing regimens or EFV-containing regimens. Phillips and colleagues conducted a study among 2203 patients in EuroSIDA who began a regimen with nevirapine or efavirenz after July 1997 (Phillips, 2001). A total of 1325 patients initiated NVP and 878 EFV. During a median of 8 months follow-up, 669 patients experienced virological failure giving an overall rate of 0.48 per year (0.83 per year if excluding those in first 6 months of follow-up who had baseline viral load >500

copies/ml). A total of 505 people on a NVP regimen experienced virological failure compared with 164 people on an EFV regimen, giving incidence rates of 0.55 per personyear and 0.35, respectively. A more recent EuroSIDA analysis examined virological outcome and drug resistance in 759 patients starting NNRTI-containing regimens (Bannister, 2008). A total of 287 (78.3%) of the 389 NVP patients and 168 (45.4%) of the 370 EFV patients experienced virological failure. NNRTI-resistant HIV was detected in 3% of patients at baseline. Out of the 131 patients still on an NNRTI and with resistance test results available at time of virological failure, NNRTI resistance was detected in 86% of patients and was similar between groups. The high levels of NNRTI resistance suggest that these drugs fostered selection pressure, and that patients had actually adhered to their regimens.

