2. OVERVIEW OF STUDY DESIGN

2.1. Study Design

This DUS will be implemented in one or more large HIV cohorts established in Europe. Data will be collected longitudinally and recorded in the HIV cohorts' databases. A minimum of six hundred patients will be entered into the study based on the prescribing of RPV-containing regimens, either as a single agent or as a FDC. An additional minimal number of 600 patients will be entered into the study based on the prescribing of EFV-containing regimens. Retrospective data available in the HIV cohorts will be used to describe patient clinical characteristics prior to receipt of RPV-containing regimens.

Data will be collected in an observational manner such that the management of the patient is determined by the patient and the caregiver and not influenced by the DUS protocol. The DUS will evaluate care as it is provided. It will capture data on a heterogeneous population treated with RPV-containing regimens or EFV-containing regimens in a comprehensive manner without exclusions to assure representativeness of the populations treated with RPV or EFV-containing regimens.

All patients initiating RPV treatment will be eligible for inclusion in the DUS. Patients initiating EFV treatment will also be eligible for inclusion in the comparator group based on the date of EFV treatment initiation. Relevant IRB/EC and HA approvals will be secured prior to initiating the study.

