3.1.1. Inclusion Criteria

Patients who initiate therapy with RPV or EFV-containing regimens during the study period will be identified. Initiation of therapy is defined as first prescription for RPV or EFV-containing regimens documented in the HIV cohort. Patients will be included in the study if they meet all of the following criteria:

- Have documented enrollment in the HIV cohort database prior to the start of RPV or EFV-treatment regimens;
- Have received at least one prescription for RPV-containing regimens or EFVcontaining regimens

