3.1.2. Exclusion Criteria

No specific exclusion criteria will be applied in this study.

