will be assigned a propensity score ranging from 0 to 1 that represents the fitted probability of receiving RPV-containing regimens. The scores from EFV-treated patients will be plotted against those for RPV-treated patients. Overlap in the treatment groups based on sample size estimates of approximately 600 patients per treatment group in the propensity space must exist for a comparison of outcomes of interest between the two groups.

Incidence rates of virologic failure, pre-treatment resistance, and treatment-emergent resistance will be calculated for the RPV and EFV-exposed patients. The three primary event rates of interest (incidence rates of virologic failure, pre-treatment resistance, and treatment-emergent resistance) will be analyzed in 3 separate sets of analyses. Additional descriptive analyses will include incidence rates for each drug calculated by dividing the number of events by the total person-exposure time and expressed as the number of events per person-year, and 95% confidence intervals. Analyses of virologic failure will be stratified by HIV treatment status (naïve/experienced) at treatment initiation.

Relative risks comparing the RPV-containing regimens with EFV-containing regimens and 95% confidence intervals will be calculated and appropriate stratified analyses will be conducted for virologic failure and emergence of treatment resistance. Poisson regression models will be used to adjust for the appropriate factors that influence the risk of virologic failure and treatment-emergent resistance. Adjustments for imbalances between the treatment groups before receiving the first dose of RPV or EFV-containing regimens will be applied using accepted methods based on sample size availability and the observed overlap of key patient characteristics based on propensity score construction.

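### Recorded prior EFV use can occur only among RPV initiators, so outside the naïve stratum the RPV-EFV ratios mix drug effect with EFV history

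*Protocol*

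**What the plan says.** Section 3.1 defines two inception groups, one new to RPV and one new to EFV. For the second it says: "Patients eligible for the comparator cohort must be new users of EFV-containing regimens". Entry to the RPV group is otherwise open. Section 2.1 states "All patients initiating RPV treatment will be eligible for inclusion in the DUS" and Section 3.1.2 states "No specific exclusion criteria will be applied in this study". Section 3.1.1 fixes how new use is judged: "Initiation of therapy is defined as first prescription for RPV or EFV-containing regimens documented in the HIV cohort". EFV starters count only from the time RPV is available in their cohort (Section 3.1).

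Section 4.5.3 plans RPV-EFV relative risks with 95% confidence intervals, Poisson models, and adjustment guided by a propensity score for which the groups must overlap. On strata it says "Analyses of virologic failure will be stratified by HIV treatment status" (naïve or experienced at initiation). More generally, "appropriate stratified analyses will be conducted for virologic failure and emergence of treatment resistance".

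Prior antiretroviral use is described as a secondary objective (Section 1.3.2) and listed among the outcome measures (Section 4.2.2), so the variable is available. It is not named as a restriction, stratum or propensity covariate for the RPV-EFV comparison. The confounder list in Section 4.2.4, which is open-ended, names neither prior EFV nor prior NNRTI use.

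**The concern.** A treatment-experienced patient who took EFV earlier, and either switched while suppressed or failed on it, qualifies for the RPV group on starting RPV. The same patient, restarting EFV, is not a new user and cannot enter the comparator. The mirror case, earlier RPV use in an EFV starter, has little room to arise because the study begins when RPV becomes available.

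Prior EFV use plausibly affects both outcomes. Suppressed switchers would lower the RPV failure rate. Patients who failed EFV may carry NNRTI mutations and would raise it. The protocol's background reports, for patients still on an NNRTI and tested at failure, that "NNRTI resistance was detected in 86% of patients and was similar between groups". The two ratios could therefore reflect who was moved to RPV rather than how RPV performs. Experienced RPV starters are expected: the naïve share is itself a primary proportion, and Section 4.2.2 has a separate failure rule for patients undetectable at baseline.

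**Working it through.** **Figures in the protocol.** None bears on this comparison. Section 4.1 covers the precision of proportions and the power of the case-control study. Its precision entry reproduces: 1.96 × √(0.95 × 0.05 / 600) = 0.0174, given as 0.02.

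**Step 1: who can enter.**

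| | Recorded prior EFV | No recorded prior EFV |
|---|---|---|
| RPV group | allowed | allowed |
| EFV group | not possible | allowed |

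Given recorded prior EFV, the probability of being in the RPV group is 1. There are no EFV comparators for these patients to match, weight or model against.

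**Step 2: the planned safeguards.**
- The naïve/experienced split puts every prior-EFV patient in the experienced stratum. The naïve stratum is clean; the experienced stratum holds the whole imbalance. The split is stated for virologic failure; for resistance the strata are not named.
- A propensity score without prior EFV can show good overlap while the imbalance remains. A score that includes it places these patients at 1, outside overlap. That helps only if they are then dropped.
- Section 5 assumes that unmeasured or missing confounders are equally distributed. That cannot cover a recorded factor which the eligibility rules make unequal.

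**Step 3: experienced stratum, no drug difference.** Assumed, since the protocol gives no values: 12-month failure of 10% without prior EFV; share q of experienced RPV starters with prior EFV; failure risk r in those patients. Ratio = [q·r + (1 − q)·0.10] / 0.10.

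| q | r = 4% | r = 20% | r = 30% |
|---|---|---|---|
| 0.25 | 0.085/0.10 = 0.85 | 0.125/0.10 = 1.25 | 0.150/0.10 = 1.50 |
| 0.50 | 0.070/0.10 = 0.70 | 0.150/0.10 = 1.50 | 0.200/0.10 = 2.00 |

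**Step 4: unstratified.** With share f of the whole RPV group having prior EFV and rate multiplier m (both assumed), ratio = (1 − f) + f·m.

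| f | m = 0.5 | m = 2 | m = 3 |
|---|---|---|---|
| 0.1 | 0.95 | 1.10 | 1.20 |
| 0.3 | 0.85 | 1.30 | 1.60 |
| 0.5 | 0.75 | 1.50 | 2.00 |

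**Step 5: simulation of the adjustments.** 400,000 patients, true ratio 1.00. Half are experienced; 40% of those have prior EFV and all start RPV; everyone else starts RPV with probability 0.45. The base failure rate is 0.35 per person-year (the EFV rate in a cohort study cited in Section 1.1), times 1.3 if experienced and times 2 if prior EFV, with 12 months of follow-up. Prior EFV is then present in 36% of the RPV group and 0% of the EFV group.

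| Estimate | Rate ratio |
|---|---|
| Crude | 1.42 |
| Naïve stratum | 1.00 |
| Experienced stratum | 1.56 |
| Weighted on naïve/experienced only | 1.29 |
| Prior-EFV patients dropped, then weighted | 1.00 |

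The crude figure also contains the ordinary imbalance in experienced status; the weighted 1.29 does not.

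**Step 6: precision cost of restricting.** At 0.35 per person-year the 12-month risk is 1 − exp(−0.35) = 0.295, or about 177 failures in 600. The 95% confidence factor is exp[1.96·√(1/e₁ + 1/e₀)], where e₁ and e₀ are the RPV and EFV failures.

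| f removed | RPV patients | RPV failures (EFV 177) | Factor |
|---|---|---|---|
| 0 | 600 | 177 | 1.23 |
| 0.1 | 540 | 159 | 1.24 |
| 0.3 | 420 | 124 | 1.26 |
| 0.5 | 300 | 89 | 1.29 |

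At the 10% risk of Step 3, 60 against 60 failures gives exp(1.96·√(2/60)) = 1.43. With half the RPV group removed, 30 against 60 gives exp(1.96·√(1/30 + 1/60)) = 1.55.

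**The case against.** The strongest reply is that this concerns one stratum of unknown size in a study that calls itself descriptive (Section 4.3.1). RPV is indicated for treatment-naïve patients, EFV is included for context, and Section 5 already warns of channelling. Covariates, strata and trimming rules are normally left to a statistical analysis plan, and nothing in the protocol prevents one from restricting the comparison. Most of this stands, and it limits the weight of the point. It does not remove it: the asymmetry comes from the protocol's own eligibility rules, the ratios are planned, and Section 5 does not name this mechanism.

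Four stronger readings are tempting, and the document supports none of them.
- A reader might infer that the ratios set EFV-experienced against EFV-unexposed patients. They do not: the RPV group is a mix, and the naïve stratum has no such patients.
- A reader might infer that no propensity score can repair the comparison. That is true for an effect in the whole RPV group. A score that includes prior EFV, followed by trimming to overlap, gives a valid ratio among EFV-unexposed patients (Step 5), and Section 4.5.3 does require overlap.
- A reader might infer that earlier EFV use is strictly impossible in the comparator. New use is judged on prescriptions documented in the cohort, so unrecorded EFV use can still enter.
- A reader might take the 86% figure as a measure of the bias. It covers 131 patients still on an NNRTI and tested at failure, across nevirapine and EFV, and says nothing about how many RPV starters had failed EFV. Mutations found before RPV are also analysed separately as pre-treatment resistance, so carrying them does not by itself inflate the treatment-emergent ratio. Only where no pre-treatment test is documented could an older mutation be counted as new.

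**Conclusion.** The point holds for the experienced stratum and for any unstratified RPV-EFV ratio. There, recorded prior EFV use lies on one side by design, and the stated stratification does not remove it. The naïve-stratum ratio is sound on this point.

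Neither size nor direction can be determined from the document. The illustrative ranges (0.70 to 2.00 within the experienced stratum, 0.75 to 2.00 unstratified) rest wholly on assumed shares and failure rates, concern virologic failure only, and show that a bias in either direction is possible, not that it is likely to be large. The structural imbalance does not depend on those assumptions. This is a cheap improvement to the comparative analysis and does not undermine the utilisation objectives.

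**What to change.** In Sections 3.1 and 4.5.3, state that the RPV-EFV comparative analyses (propensity score, relative risks and Poisson models) are restricted to patients with no recorded use of RPV or EFV before the index date. Keep all RPV initiators in the utilisation, SmPC and descriptive analyses. Report virologic failure and RAM rates for RPV initiators with prior EFV as a separate, RPV-only stratum.

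This needs a sentence in each section and one extra table, and uses treatment history already collected. The price is fewer experienced RPV patients in the comparison and a somewhat wider interval (Step 6). The loss falls entirely on the experienced stratum, where the relative widening will be greater than in the whole-group figures. EFV use that a cohort never recorded would remain undetected.

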3.1.1. Inclusion Criteria

Patients who initiate therapy with RPV or EFV-containing regimens during the study period will be identified. Initiation of therapy is defined as first prescription for RPV or EFV-containing regimens documented in the HIV cohort. Patients will be included in the study if they meet all of the following criteria:

- Have documented enrollment in the HIV cohort database prior to the start of RPV or EFV-treatment regimens;
- Have received at least one prescription for RPV-containing regimens or EFVcontaining regimens

3.1.2. Exclusion Criteria

No specific exclusion criteria will be applied in this study.

3.1.3. Data Source(s)3.1.3.1. Feasibility Assessment of European databases

An evaluation will be conducted of the following available HIV cohorts in Europe for their suitability for meeting the study objectives:

- EuroSIDA
- UK Collaborative HIV cohort (CHIC), with linkage to the UK HIV drug resistance database and the UK Register of HIV Seroconverters
- Danish HIV cohort
- German HIV-1 Seroconverter cohort
- Italian Antiretroviral Resistance Cohort Analysis database (ARCA)
- French Hospital Database on HIV (FHDH)
- Cohort of Spanish AIDS Research Network (CoRIS)

4. STATISTICAL METHODS

4.1. Sample Size and Study Precision

4.1.1. DUS Sample Size and Study Precision

The sample size targets will produce an error rate of no more than 5%. A minimum of 600 patients exposed to RPV-containing regimens will be included in the DUS to assess the proportion of appropriate use of RPV formulations. The error rate under these assumptions and an observed proportion of appropriate use of 95% is estimated at \pm -0.02.

Proportion		
of	95% CI	95% CI
appropriate	error (+/-)	error (+/-)
use (%)	with 400	with 600
	patients	patients
70	0.04	0.04
75	0.04	0.03
80	0.04	0.03
85	0.03	0.03
90	0.03	0.02
95	0.02	0.02

4.1.2. Nested Case-Control Sample Size

The power and detectable odds ratio for the nested case-control study will be based on the number of patients experiencing virologic failure while under observation in the DUS. The power ranges for detectable odds ratios based on the observed number of cases at alpha=0.05 is given Table 1 below. For example, based on an alpha of 0.05, a control to case ratio of 4:1, and an adherence level of 80% or greater in 50% of patients, approximately 40 cases would be needed for a minimally detectable odds ratio of 3.0 with 80% power. For a minimally detectable odds ratio of 2.0, approximately 90 cases would be needed.

Table 1. Sample size and study power for minimally detectable odds ratio assuming a two-sided test, 5 percent alpha level, an adherence level of 80% or greater in 50% of patients, and a 4:1 ratio of controls to cases.

Detectable OP								
$\frac{\text{Detectable OR}}{25} = 25 \qquad 4 \qquad 5$								
Cases	1.5	2	2.5	3	5.5	4	5	
0	0.0249979	0.0249979	0.0249979	0.0249979	0.0249979	0.0249979	0.0249979	
10	0.0788996	0.1456193	0.2129961	0.2757540	0.3321963	0.3821915	0.4649655	
20	0.1199695	0.2577778	0.3968270	0.5174057	0.6151327	0.6920104	0.7982529	
30	0.1603557	0.3671945	0.5590526	0.7033559	0.8024057	0.8678758	0.9386928	
40	0.2006102	0.4692415	0.6894629	0.8283160	0.9066258	0.9489490	0.9838703	
50	0.2406664	0.5610976	0.7878403	0.9052049	0.9585720	0.9817546	0.9961780	
60	0.2803320	0.6415215	0.8586668	0.9496126	0.9825155	0.9938649	0.9991643	
70	0.3193976	0.7103878	0.9078456	0.9740491	0.9929161	0.9980363	0.9998286	

0.3576683 0.7682871 0.9410123 0.9869870 0.9972264 0.9993967 0.9999667 80 0.9999938 90 0.3949750 0.8162206 0.9628471 0.9936230 0.9989453 0.9998210 0.9999989 100 0.9969370 0.9996089 0.9999484 0.4311767 0.8553823 0.9769310

Measurements 4.2.

4.2.1. **Exposure Definition and Measures**

Exposure to RPV will be determined by the presence of prescription records for the FDC of FTC/RPV/TDF or single agent of RPV among patient data. Relevant drug codes will be used to identify RPV-containing regimens in the HIV cohorts. The baseline date for exposure follow-up (index date) for a patient within a given treatment group will be defined by first prescription of RPV or EFV-containing regimens. Duration of exposure will be based on dispense date and days of supply for each dispensed prescription. Exposure to RPV or EFV-containing regimens will be considered discontinued if the prescription is not refilled within a specified interval of time (e.g. twice the days' supply) of the previous prescription. Switches from one drug to another will be captured and time on drug will be defined by the exposure periods. The total length of exposure to a given drug will be the time between start and stop periods of exposure to the same drug.

4.2.1.1. **Exposure Definition in Nested Case-Control Study**

For the nested case-control analysis, exposure will be based on 1) level of daily medication adherence, and 2) level of adherence to food recommendations. Cases and matched controls that are selected will be asked to retrospectively report via a questionnaire how often they took their HIV medication during a specified time period and how often RPV was taken with food. A single item querying the number of prescribed doses the participant had missed in a specified time period will be used, as follows:

"How many doses of your complete HIV regimen did you miss in the last 7 days?"

"For those days you missed, what component of your HIV regimen did you miss?" (If applicable)

"How often did you take RPV with food in the last 7 days?"

Since RPV dosing is once-daily, number of doses taken is equivalent to number of days the medication is taken. A 7-day recall period is proposed for this analysis as it has the advantage of including a weekend, during which adherence is often problematic. Further, DATE (6 September 2011) 20

longer recall periods (7-day vs. 1-3 day) may yield more useful data for once-daily ART dosing since there are too few dosing times in a very brief recall period to capture variations in adherence behaviors (Simoni, 2006).

Level of daily medication adherence will be expressed as a continuous measure of percentage of doses taken calculated as [(prescribed doses – missed doses)/prescribed doses x 100]. Level of adherence to dietary instructions will be estimated based on appropriate use; the proportion of doses taken that were accompanied by food calculated as [(doses taken with food/total doses taken) x 100]. Adherence data will then be converted to dichotomous indicators of adherent versus nonadherent patients. The cut-off threshold is arbitrary and has ranged from 75% to 100% in the published literature (Simoni, 2006; Wilson, 2009). Based on findings from a meta-analysis, Nieuwkerk and Oort suggest that for thresholds determined a priori, choosing a threshold below 95% would be more appropriate (Nieuwkirk and Oort, 2005). For this analysis, patients who have greater than an 80% level of adherence will be categorized as adherent. Patients will be classified as adherent vs. nonadherent with respect to treatment adherence and adherence to food recommendations, separately based on the 80% level of adherence.

